3. SUMMARY OF STUDY DESIGN

[figure not shown]
This Phase 4, double-blind, randomized, placebo-control, multicenter study will evaluate the effect of OCA on clinical outcomes in subjects with PBC who are at higher risk of liver-related clinical complications.

Eligible subjects will have a diagnosis of PBC with bilirubin levels $>ULN$ and $\leq 5x ULN$ and/ or $ALP > 3x ULN$. Subjects will be screened twice during a 1- to 8-week Screening period prior to entering the study to allow for the collection of repeat serum chemistry samples (at least 2 weeks apart) to confirm pretreatment alkaline phosphatase (ALP) and total bilirubin values.

Investigational product (IP) will be taken orally, once daily for the majority of subjects; dose and frequency will be modified for subjects with cirrhosis (including subjects progressing to cirrhosis during the study) and classified as Child-Pugh B or C. The randomization will be stratified by ursodeoxycholic acid (UDCA) treatment (yes/ no) and baseline bilirubin categories ($>$ upper limit of normal [ULN]/ $\leq ULN$). A minimum of 30% of subjects will have elevated bilirubin ($>ULN$) at Screening.

The study is event driven and will continue until approximately 127 adjudicated primary endpoint events have been accrued in unique subjects, or until the Sponsor (eg, based on a recommendation from the Data Monitoring Committee (DMC)) terminates the study. Subjects are expected to be followed for a minimum of approximately 6 years. Figure 1 below displays the study design diagram. Schedules of study procedures are outlined in Table 1 (Screening to Month 12) and Table 2 (Year 2 to End-of-Study Endpoints) of the study protocol, where more details are provided.

Figure 1: Schematic Diagram Study 747-302

EOS = end of study; M = month, OCA = obeticholic acid; ULN = upper limit of normal
 Initial dose titration of investigational product should occur at the Month 3 visit, or any study visit thereafter for subjects on all dosing regimens, based on tolerability and biochemical response (Up-titration should be considered when ALP and/ or total bilirubin are $>ULN$). Subsequent dose titration(s) for subjects classified as Child Pugh B or Child-Pugh C and following a modified dosing schedule may occur no earlier than 6 weeks after the previous dose titration.

Dosing frequency will be determined by the presence or absence of cirrhosis and, if cirrhosis is present, by Child-Pugh Score as described below:

	Planned Dosing Regimen	

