8.3.2. Liver Biochemistry Analyses

Analyses of changes in liver biochemistry (gamma-glutamyl transferase (GGT), ALT, AST, conjugated bilirubin, albumin, and INR) at each visit will be compared between treatment groups using a restricted maximum likelihood based mixed-effect model repeated measures (MMRM) with treatment, baseline, visit, visit by treatment interaction and randomization stratification factors to be included in the model. Visits through Month 24 will be included. An unstructured covariance model will be used. If the computational algorithm fails to converge, the following structures will be tested in the order: Toeplitz, AR(1) and compound symmetry (CS). If the model still does not converge, the stratification factors will be dropped from the model one at a time (UDCA followed by bilirubin).

Change from Baseline over time will be analyzed using analysis of covariance (ANCOVA) with change from Baseline as the dependent variable including treatment group and randomization stratification factor as fixed effects and the Baseline values as a covariate. Descriptive statistics of the laboratory values will be summarized by treatment group. The results, change from

Baseline, and percentage change from Baseline values, as well as estimates of least-square means, standard errors, and 95% CIs, will be presented by treatment group. Estimates of the mean difference between treatment groups, the standard error of the difference, and 95% CI of the difference will be presented.

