8.7. Subgroup Analyses of Efficacy

The primary and all key secondary efficacy endpoints ([Section 8.2](#)), liver biochemistry ([Section 8.3.2](#)), and prognostic endpoints and markers of inflammation endpoints ([Section 8.3.3](#)) will be analyzed for subject subgroups based on the ITT population. Sensitivity analyses will not be run for subgroup analyses. Subgroups will be assessed at Baseline. Baseline subgroups of interest are as follows:

- Baseline disease stage:
 - On-label per United States Prescribing Information (USPI). The on-label subgroup includes ITT subjects who had not experienced clinically evidence portal hypertension (CSPH) or decompensation at baseline.
 - A subject is defined to have CSPH at baseline if they had any of the following: a previous history of portal hypertension includes procedures for TIPS, sclerotherapy, ligation, HVPG measurement >10 mmHG, paracentesis, thoracentesis (due to hepatic hydrothorax); previous history or baseline observation of preferred terms for presence of collateral circulations secondary to CSPH, GI bleeding due to varices or portal hypertension, gastroesophageal varices without bleeding and portal hypertensive gastropathy, ascites, hepatopulmonary syndrome,

hepatorenal syndrome, portopulmonary hypertension, hepatic encephalopathy; platelets $<150 \times 10^9/L$ with splenomegaly and/or with transient elastography >15 kPa.

- A subject is defined to have decompensation at baseline if they had any of the following: a Child-Pugh score of B or C; previous history or baseline observation of preferred terms for gastric variceal or esophageal variceal bleeding, ascites, hepatic hydrothorax, spontaneous bacterial peritonitis, hepatic encephalopathy, hepatorenal / hepatopulmonary / portopulmonary syndrome, prior TIPPS or other peritoneovenous shunt.
 - Compensated, non-cirrhosis or cirrhosis. The pre-decompensation subgroup includes ITT subjects who had not experienced decompensation at baseline.
 - Decompensated. The decompensated subgroup includes ITT subjects who had experienced decompensation at baseline.
 - Contraindicated per USPI. The contraindicated subgroup includes ITT subjects who had experienced CSPH and/or decompensation at baseline.

The primary efficacy endpoint and key secondary endpoints will also be assessed for the following baseline subgroups of interest if there are a sufficient number of subjects in each group (eg, >5 subjects per group):

- Sex: male, female

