9.4. Clinical Laboratory Evaluations

Laboratory parameters will be summarized in both conventional units and the standard international (SI) system of units using the Safety Population by treatment group and descriptive statistics at Baseline and at each scheduled study visit. Only central laboratory data will be used.

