9.4.2. Chemistry

Descriptive statistics will be used to summarize the results and change and percentage change from Baseline to each on-study evaluation visit for albumin, blood urea nitrogen, creatinine, total bilirubin, unconjugated (indirect) bilirubin, conjugated (direct) bilirubin, GGT, AST, ALT, ALP, electrolytes (calcium, chloride, potassium, sodium), magnesium, phosphorous, bicarbonate,

glucose, total protein, total cholesterol, low-density lipoprotein, high-density lipoprotein, very low density lipoprotein (VLDL), triglycerides, free fatty acids.

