Percentages based on frequency counts will be based on available data, and denominators will generally exclude missing values, unless otherwise stated. For frequency counts of categorical variables, categories whose counts are zero will be displayed for the sake of completeness. For example, if none of the subjects discontinued due to “lost to follow-up,” this reason will be included in the table with a count of 0. Percentages based on frequency counts will be presented as a whole number (no decimal places), and values less than 1% will be presented as “<1%.” Values less than 100% but that round up from 99.5% to 100% will be presented as “>99%.”

Quantitative laboratory tests containing less than (<) and greater than (>) symbols are test results that are below and above quantifiable limits, respectively. In order to retain these values for analysis purpose, the following imputations will be done within the analysis datasets:

For laboratory test results that are below the quantifiable limit:

Imputed laboratory results = (numeric portion of the result) x 0.9.

For laboratory test results that are above the quantifiable limit:

Imputed laboratory results = (numeric portion of the result) x 1.1.

For the purpose of tabulations, the unscheduled post-baseline values generally will be excluded from summary tables, but will be included in data listings. Unscheduled visits will be considered for analyses of shift from baseline to worst value (low-normal-high).

Standard Calculations

Variables requiring calculation will be derived using the following formulas:

- First dose date is defined as the day of first dose of IP received after randomization
- Last dose date is defined as day of the last dose of IP
- Time to event – The time to an event will be calculated in days as the date of the first occurrence of the event minus the date of first investigational product administration plus 1
- Days – A duration expressed in days between one date (*date1*) and another later date (*date2*) will be calculated using the following formulas:

duration in days = $date2 - date1 + 1$, where $date1 \geq$ first dose date

duration in days = $date2 - date1$, where $date1 <$ first dose date

- Months – A duration expressed in months is calculated as the number of days divided by 365.25/12 (approximately 30.4)
- Years – A duration expressed in years between one date (*date1*) and another date (*date2*) is calculated using the following formulas:

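### The one worst-value laboratory analysis the SAP names is a low-normal-high shift, which cannot grade further rises in an ALP or bilirubin already high at entry, nor the size of ALT and AST rises

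*SAP*

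**What the plan says.** Section 9.4 plans laboratory safety as "descriptive statistics at Baseline and at each scheduled study visit", by arm in the Safety Population, from central laboratory data only. Section 9.4.2 applies this to the liver tests: "Descriptive statistics will be used to summarize the results and change and percentage change from Baseline to each on-study evaluation visit for albumin", and the list goes on to total, direct and indirect bilirubin, AST, ALT and ALP. Neither section mentions a shift table, a peak value or a ULN multiple.

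Appendix A, Data Conventions, then states that "the unscheduled post-baseline values generally will be excluded from summary tables", with such values kept in listings. The one exception it gives is this: "Unscheduled visits will be considered for analyses of shift from baseline to worst value (low-normal-high".

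The population is fixed in section 3: "Eligible subjects will have a diagnosis of PBC with bilirubin levels" above ULN and up to 5x ULN, and/or ALP above 3x ULN. On bilirubin alone, "A minimum of 30% of subjects will have elevated bilirubin" at Screening.

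**The concern.** A low-normal-high scale has cut-points only at the two normal limits. It works for an analyte that is normal at baseline and for which any departure matters. It cannot register worsening in a test that is already above ULN, and it does not grade how far above ULN a test has gone. ALP and bilirubin define entry to this trial, so they are the tests most affected.

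At stake is a safety comparison: how many subjects in each arm had a large rise in a liver test at any time. The question matters in subjects at higher risk of liver complications, where dosing is reduced for Child-Pugh B and C and hepatic events are of special interest. The one analysis that expressly brings in unscheduled results cannot answer it.

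**Working it through.** No sample size, power or alpha figure is involved, so there is no SAP number to reproduce. The check is category logic, a count of who is affected, and a test of whether other planned analyses fill the gap.

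**Step 1: category logic.**

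| Test | Baseline | Worst value | Shift cell |
|---|---|---|---|
| ALP | 3.1x ULN | 3.2x ULN | high to high |
| ALP | 3.1x ULN | 9.3x ULN (3 × 3.1) | high to high |
| ALT | normal | 1.1x ULN | normal to high |
| ALT | normal | 10x ULN | normal to high |

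**Step 2: who starts high.** By the entry rule, every eligible subject does for ALP, bilirubin or both. This assumes that screening values persist to the last pre-dose evaluation, which is the Appendix A baseline for qualitative parameters. The Clinical Pharmacology Analysis Plan (section 5) gives about 334 enrolled. If the 30% minimum were only just met (the actual share is not given), 0.30 × 334 ≈ 100 would start with high bilirubin. For the other 234 or so the bilirubin shift is informative, but their ALP must have been above 3x ULN.

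**Step 3: do the bilirubin and MELD components cover the gap for bilirubin?** ULN for bilirubin is not stated; I assume 1.0 to 1.3 mg/dL. The entry cap is then 5 × 1.0 = 5.0 to 5 × 1.3 = 6.5 mg/dL. A subject already above 3 mg/dL cannot newly cross the Group 2 threshold, which in any case applies only without baseline decompensation.

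For MELD, Appendix A gives, with aetiology 0 for cholestatic disease:

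MELD = 3.78 ln(bilirubin) + 11.2 ln(INR) + 9.57 ln(creatinine), with values below 1.0 set to 1.0.

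At INR 1.0, creatinine up to 1.0 mg/dL and sodium at least 137 mmol/L (so MELD-Na equals MELD):

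- Tripling bilirubin adds 3.78 × ln 3 = 4.15 points.
- From 5.0 to 15.0 mg/dL: 6.1 to 10.2. From 6.5 to 19.5 mg/dL: 7.1 to 11.2. Neither reaches 15.
- Reaching 15 needs exp(15/3.78) = 52.9 mg/dL; at INR 1.2, exp((15 − 11.2 ln 1.2)/3.78) = 30.8 mg/dL.

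The component is far more sensitive when sodium is low. At sodium 130 mmol/L and INR 1.0, MELD-Na of 15 needs MELD = (15 − 1.32 × 7)/(1 − 0.033 × 7) = 5.76/0.769 = 7.49, so bilirubin = exp(7.49/3.78) ≈ 7.3 mg/dL.

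**Step 4: the other planned analyses.**

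| Analysis | What it gives | What it leaves out |
|---|---|---|
| 9.4 tables with the Appendix A statistics | Per-visit minimum and maximum of result, change and percentage change, by arm | Counts of subjects; a subject's peak across visits; generally, unscheduled values |
| 8.3.2 models | Mean changes in GGT, ALT, AST, conjugated bilirubin, albumin and INR ("Visits through Month 24 will be included" in the repeated-measures model), repeated by disease stage under 8.7 | ALP and total bilirubin; individual extremes |
| 8.4.2 responder counts | Percentages by arm and visit against ULN multiples of ALP, AST and bilirubin | Size of a rise: failing ALP ≤1.76x ULN does not separate 3.1x from 9.3x; no ALT |
| 8.3.3 | MELD and Child-Pugh change at annual timepoints | Individual enzymes; values between those timepoints |
| 9.2 adverse events, including hepatic AESIs; 9.8 by stage | Reported terms, with abnormal laboratory findings eligible | Systematic laboratory magnitude |

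Each contributes something. None tabulates peak liver-test rises by size, by arm, across scheduled and unscheduled results.

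**The case against.** The strongest reply is that the quoted sentence is a data-handling convention and not the liver-safety analysis. It says where unscheduled values may enter; it does not say low-normal-high is the only permitted scale, and section 9.4 contains nothing false. Table shells are mentioned in Appendix A but not shown, so richer outputs may exist. This stands as a limit: the point concerns the SAP text only. But the text does name a scale for worst values, and that scale is ill-suited to the tests that define entry.

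A second reply is that large rises are not invisible. This also stands in part. A scheduled ALP moving from 3.1x to 9.3x ULN is a 200% increase and would set or be exceeded by that visit's maximum percentage change in its arm. Responder counts, adverse event reports and the composite components add to this, and unscheduled values are listed. What remains missing is narrower: counts of subjects by size of peak rise, with unscheduled values included.

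Third, the bilirubin example is demanding. It needs entry at the cap, a tripling, and normal INR, creatinine and sodium together. That is fair; the sodium calculation shows how quickly the MELD-Na component becomes sensitive otherwise. The ALT, AST and ALP limits do not depend on this example.

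A reader might infer that the plan would conceal hepatotoxicity, or that large rises mostly surface at unscheduled visits. The documents support neither. The per-visit maxima and the other routes contradict the first, and nothing in the SAP says when large rises tend to be found.

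**Conclusion.** The point holds as a minor weakness in a descriptive safety analysis. The only worst-value laboratory analysis named uses a scale that cannot grade further rises in whichever of ALP and bilirubin is high at entry, and cannot separate small from large ALT and AST rises. By the entry rule this touches every eligible subject for at least one test, provided that screening values carry to baseline. The bilirubin shift remains useful for those entering with a normal value. The bilirubin figures rest on the assumed ULN of 1.0 to 1.3 mg/dL and on the stated INR, creatinine and sodium conditions. No test, estimate or error rate is affected.

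**What to change.** In section 9.4.2 and the matching Appendix A sentence, for ALT, AST, ALP and total and conjugated bilirubin, replace the low-normal-high shift with each subject's worst post-baseline value. Take it from all scheduled and unscheduled central results within the section 9 safety window (through 30 days after stopping treatment, excluding data after commercial OCA starts).

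- Categorise ALT and AST by multiples of ULN.
- Categorise all five tests by multiples of the subject's own baseline (for example >2x, >3x, >5x). This matters most for ALP and bilirubin.
- Present by arm and by the baseline disease stages of section 8.7.
- Add a plot of peak ALT/AST against peak total bilirubin, both in multiples of baseline.
- Keep low-normal-high for the other analytes.

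The cost is a few more descriptive tables and one figure from central data already collected. Data collection and all inferential analyses stay as they are.

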8.4. Exploratory Efficacy Analyses

8.4.1. Acute-on-Chronic Liver Failure (ACLF)

Shift tables (i.e., status at baseline versus status at follow-up visit) will be presented for the Chronic Liver Failure Consortium Acute Decompensation score (CLIF-C ADs) using the categories: CLIF-C ADs ≤ 45 , $45 < \text{CLIF-C ADs} \leq 60$, and CLIF-C ADs > 60 . The number and percentage of subjects in each category will be presented by treatment group and visit.

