Moderate - Total Bilirubin > ULN and Albumin ≥ LLN or

Total Bilirubin \leq ULN and Albumin $<$ LLN

Severe – Total Bilirubin $>$ ULN and Albumin $<$ LLN, where baseline values of total bilirubin and albumin are taken to be the average of all pre-dose measurements.

- The CLIF-C ADs is derived using the following formula:

$$\text{CLIF-C ADs} = 10 \times 0.03 \times [\text{Age (years)}] + 0.66 \times \ln[\text{creatinine (mg/dL)}] + 1.71 \times \ln[\text{INR}] + 0.88 \times \ln[\text{WBC (} 10^9 \text{ cells/L)}] - 0.05 \times [\text{sodium (mmol/L)}] + 8.$$

Inverse Probability of Censoring Weighting

The hazard ratio will be estimated using Inverse Probability of Censoring Weighting (IPCW) techniques (Robins 1999). Baseline predictors of both censoring and clinical outcome will be identified in advance. Augmented IPCW estimators described by Robins may be implemented to explore the possible impact of unmeasured confounding. Baseline predictors of both censoring and clinical outcome for the IPCW analysis are:

- Treatment Group: OCA/Placebo
- Age (year) at Screening Visit
- Sex: Male/Female
- UDCA use at Screening Visit: Yes/No
- Liver biochemistry at Baseline (alkaline phosphatase (ALP) (U/L), alanine transaminase (ALT) (U/L), aspartate transaminase (AST) (U/L), total bilirubin ($\mu\text{mol/L}$), albumin (g/L), and platelets)

The post-baseline time-varying covariates are ALP, ALT, AST, total bilirubin, and AE of pruritus with severity of moderate and severe.

To derive the IPCW weights, the patient's follow-up time up until the time of censoring or event occurring will be partitioned into about 10 intervals. The probability of remaining uncensored at the end of each time interval adjusted for baseline variables, and post-baseline time-varying covariates will be estimated using a pooled logistic regression model. To avoid possible extreme values when taking the inverse of the estimated probabilities from the pooled logistic model with both baseline and time-varying post-baseline covariates, the inverse of these probabilities will be stabilized by multiplying the probability of remaining uncensored conditional only on baseline covariates. Once the IPCW weights are derived, the hazard ratio of treatment effect and corresponding 95% CI will be estimated using a weighted Cox regression model with Sandwich estimator to obtain the robust estimate of the variance-covariance matrix of the parameter estimates.

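### The CLIF-C ADs formula applies its factor of 10 to the age term only, so at realistic values every subject scores 45 or below and the planned three-category shift tables cannot show anything

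*SAP*

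**What the plan says.** Section 8.4.1 of the SAP, the only analysis under the acute-on-chronic liver failure heading, plans baseline-to-visit shift tables for the "Chronic Liver Failure Consortium Acute Decompensation score (CLIF-C ADs) using the categories" ≤45, >45 to ≤60, and >60. It adds: "The number and percentage of subjects in each category will be presented by treatment group and visit".

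The score is defined in Appendix A, Standard Calculations. That list is operative: "Variables requiring calculation will be derived using the following formulas". The CLIF-C ADs entry ("The CLIF-C ADs is derived using the following formula") reads, in plain notation:

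CLIF-C ADs = 10 × 0.03 × Age + 0.66 × ln(creatinine) + 1.71 × ln(INR) + 0.88 × ln(WBC) − 0.05 × sodium + 8

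No bracket opens after the 10 and none closes after the 8.

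**The concern.** As printed, the 10 belongs to the age term alone. The score is then 0.3 points per year of age plus a small laboratory contribution, and it lies far below the cut-points of 45 and 60 that Section 8.4.1 applies to it. A multiplier written as 10 × 0.03 on a single term is also odd, because it would simply be written 0.3. A separate 10 makes sense as an outer factor.

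If the formula is programmed literally, all subjects fall in the lowest category at baseline and at every later visit, in both arms. The Data Conventions in Appendix A require categories with zero counts to be displayed, so the output would show 100% in the lowest row and zeros above it. A reader could take this for a real finding of low risk and no change, in a population that the SAP describes as being at higher risk of liver-related complications.

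**Working it through.** **Inputs.** The coefficients and the constant come from Appendix A and the cut-points from Section 8.4.1. The SAP gives no typical subject values, so age (years), creatinine (mg/dL), INR, WBC (10⁹/L) and sodium (mmol/L) are assumptions, chosen to run from normal to beyond any plausible patient.

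**Formulas.** Let L be everything except the age term:

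L = 0.66 ln(creatinine) + 1.71 ln(INR) + 0.88 ln(WBC) − 0.05 × sodium + 8

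- As printed: 0.3 × Age + L
- With the 10 applied to the whole sum: 10 × (0.03 × Age + L) = 0.3 × Age + 10 L

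The age contribution is the same in both. The printed form carries the laboratory part at one tenth of its weight.

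**One case in full.** Age 60, creatinine 0.8, INR 1.0, WBC 6, sodium 140:

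- L = −0.15 + 0 + 1.58 − 7 + 8 = 2.43
- As printed: 18 + 2.43 = 20.4
- Whole sum: 18 + 24.3 = 42.3

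**Range of cases.**

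| Age, creatinine, INR, WBC, sodium | L | As printed | Whole sum × 10 |
|---|---|---|---|
| 40, 0.7, 1.0, 5, 141 | 2.13 | 14.1 | 33.3 |
| 60, 0.8, 1.0, 6, 140 | 2.43 | 20.4 | 42.3 |
| 65, 1.2, 1.5, 8, 134 | 3.94 | 23.4 | 58.9 |
| 65, 1.5, 1.5, 8, 132 | 4.19 | 23.7 | 61.4 |
| 75, 2.5, 2.5, 15, 128 | 6.15 | 28.7 | 84.0 |
| 85, 4, 4, 25, 120 | 8.12 | 33.6 | 106.7 |
| 90, 10, 5, 50, 110 | 10.21 | 37.2 | 129.1 |
| 100, 10, 10, 50, 110 | 11.40 | 41.4 | 144.0 |

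Every value in the printed column falls in the ≤45 category. The whole-sum column reaches all three categories within the first four rows.

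**Age needed to pass the cut-points as printed**, (45 − L)/0.3 and (60 − L)/0.3:

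- Normal laboratory values (L = 2.43): about 142 and 192 years
- Severe values (L = 6.15): about 130 and 180 years
- Extreme values (L = 11.40): 112 and 162 years

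**Sensitivity to change.** As printed, doubling the INR moves the score by 1.71 × ln 2 = 1.2 points, while 20 years of age moves it by 6. A score built this way can hardly register a shift between visits, which is the purpose of the table.

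**Another possible grouping.** Applying the 10 to everything except the constant, then adding 8, equals the whole-sum value minus 72. For the 60-year-old with normal values this is 42.3 − 72 = −29.7, which does not fit the cut-points either.

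**The case against.** The strongest objection is that the missing bracket may have been lost when the PDF was converted to text. Other displayed equations show signs of such damage. Percentage change from baseline has outer parentheses in the interim SAP (Section 7.4) but appears as a fraction without them in Appendix A of the final SAP. In Section 7.5 of the interim SAP the radical appears to cover a Z-score that can be negative. A lost outer bracket therefore cannot be excluded. Against this, all inner brackets of the CLIF-C ADs formula survive, as do the grouping brackets of the MELD-Na formula shortly before it, and there is no positive sign of loss here. Looking at the original page settles the matter at once.

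Two further points stand as qualifications. First, the limit of 45 is practical and not mathematical: age 110 with creatinine 15, INR 20, WBC 100 and sodium 100 gives 33 + 13.96 = 47.0, but no such subject will be enrolled. Second, the SAP cites no source for the score, so the correct bracketing is inferred from the SAP's own cut-points and needs confirmation.

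The consequence is also limited. The score appears only in an exploratory descriptive table, with no test, and is in neither the primary nor the key secondary endpoints. A programmer might notice a table with everyone in one row. That lowers the weight of the point but does not make the formula right.

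**Conclusion.** The point holds. The printed formula and the cut-points of Section 8.4.1 cannot both be right. Over assumed inputs from normal to extreme the printed score runs from about 14 to 41, so the two upper categories would be empty and the shift tables would carry no information on treatment or time. Applying the 10 to the whole sum, constant included, gives about 33 to 84 over the first five cases in the table, and is the only grouping tried that fits the cut-points.

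This rests on assumed subject values, on the text being a faithful copy of the formula, and on the program following the SAP literally. It should be corrected, but it affects one exploratory descriptive analysis only; no confirmatory conclusion depends on it.

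**What to change.** In Appendix A, Standard Calculations, bracket the sum:

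CLIF-C ADs = 10 × [0.03 × Age + 0.66 × ln(creatinine) + 1.71 × ln(INR) + 0.88 × ln(WBC) − 0.05 × sodium + 8]

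Confirm this against the published source of the score and add that source to the SAP's references. Check that the analysis program groups the terms the same way, for example by running one or two of the cases above through it. If the tables have already been produced from the unbracketed form, rerun them and record the correction in the clinical study report.

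The cost is one pair of brackets in the SAP, one in the code if needed, and a rerun of the Section 8.4.1 tables. No additional data are required.
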